5.2 Exclusion criteria

Participants meeting any of the following criteria are not eligible for inclusion in this study.

- 1. Chest X-ray or chest MRI with evidence of ongoing infectious or malignant process, obtained within 3 months prior to screening and evaluated by a qualified physician.
- 2. Participants taking high potency opioid analgesics (e.g., methadone, hydromorphone, morphine).
- 3. Previous exposure to secukinumab or other biologic drug directly targeting interleukin-17 (IL-17) or IL-17 receptor.
- 4. Use of any investigational drug and/or devices within 4 weeks before randomization or a period of 5 half-lives of the investigational drug, whichever is longer.
- 5. Ongoing use of prohibited psoriasis treatments / medications (e.g., topical corticosteroids, UV therapy) at randomization. The following wash out periods need to be observed prior to the randomization:
 - a. Oral or topical retinoids 4 weeks
 - b. Photochemotherapy (e.g. PUVA) 4 weeks
 - c. Phototherapy (UVA or UVB) 2 weeks
 - d. Topical skin treatments (except in face, eyes, scalp and genital area during screening, only corticosteroids with mild to moderate potency) 2 weeks

- 6. History of hypersensitivity to drug of similar chemical classes as that of the study drug or its excipient.
- 7. Any intramuscular or intravenous corticosteroid treatment within 4 weeks before randomization.
- 8. Any therapy by intra-articular injections (e.g., corticosteroid) within 4 weeks before randomization.
- 9. Participants who have previously been treated with more than 3 different TNF-α inhibitors (investigational or approved).
- 10. Participants who have ever received biologic immunomodulating agents except for those targeting TNFα.
- 11. Previous treatment with any cell-depleting therapies including but not limited to anti-CD20, investigational agents (e.g., Campath, anti-CD4, anti-CD5, anti-CD3, anti-CD19).
- 12. Pregnant or nursing (lactating) women, where pregnancy is defined as the state of a female after conception and until the termination of gestation, confirmed by a positive hCG laboratory test.
- 13. Women of child-bearing potential, defined as all women physiologically capable of becoming pregnant, unless they are using effective contraception during the entire study (during the entire study).

Effective contraception is defined as either:

- Barrier method: Condom or Occlusive cap (diaphragm or cervical/vault caps) with spermicide (where available). Spermicides alone are not a barrier method of contraception and should not be used alone.
- Other more effective than the barrier method and are also acceptable:
 - a. Total abstinence: When this is in line with the preferred and usual lifestyle of the subject [Periodic abstinence (e.g. calendar, ovulation, symptothermal, post-ovulation methods) and withdrawal are not acceptable methods of contraception].
 - b. Female sterilization: have had a surgical bilateral oophorectomy (with or without hysterectomy) or tubal ligation at least six weeks before taking study treatment. In case of oophorectomy alone, only when the reproductive status of the woman has been confirmed by follow up hormone level assessment.
 - c. Use of established oral, injected or implanted hormonal methods of contraception, intrauterine device (IUD) or intrauterine system (IUS). In case of use of oral contraception women should have been stabile on the same pill for a minimum of 12 weeks before taking study treatment.

If local regulations deviate from the contraception methods listed above to prevent pregnancy, local regulations apply and will be described in the Informed Consent Form (ICF).

NOTE: Women are considered post-menopausal and not of child bearing potential if they have had 12 months of natural (spontaneous) amenorrhea with an appropriate clinical profile (e.g. age appropriate history of vasomotor symptoms) or have had surgical bilateral oophorectomy (with or without hysterectomy), total hysterectomy or bilateral tubal ligation at least six weeks ago. In the case of oophorectomy alone, only when the reproductive status of the woman has been confirmed by follow up hormone level assessment is she considered not of child bearing potential.

- 14. Active ongoing inflammatory diseases other than PsA that might confound the evaluation of the benefit of secukinumab therapy, including active IBD and active uveitis.
- 15. Underlying metabolic, hematologic, renal, hepatic, pulmonary, neurologic, endocrine, cardiac, infectious or gastrointestinal conditions which in the opinion of the investigator immunocompromises the subject and/or places the subject at unacceptable risk for participation in an immunomodulatory therapy.
- 16. Significant medical problems or diseases, including but not limited to the following: uncontrolled hypertension (≥160/95 mmHg), congestive heart failure [New York Heart Association status of class III or IV], uncontrolled diabetes.
- 17. History of renal trauma, glomerulonephritis, or subjects with one kidney only, or a serum creatinine (Scr) level exceeding 1.5 mg/dL (132.6µmol/L).
- 18. Screening total white blood cell(s) (WBC) count <3,000/µL, or platelets <100,000/µL or neutrophils <1,500/µL or hemoglobin <8.5 g/dL (85g/L).
- 19. Active systemic infections during the last two weeks (exception: common cold) prior to randomization.
- 20. History of ongoing, chronic or recurrent infectious disease or evidence of tuberculosis infection as defined by either a positive PPD skin test (the size of induration will be measured after 48-72 hours, and a positive result is defined as an induration of ≥ 5mm or according to local practice/guidelines) or a positive QuantiFERON TB-Gold test as indicated in the assessment schedule. Subjects with a positive test may participate in the study if further work up (according to local practice/guidelines) establishes conclusively that the subject has no evidence of active tuberculosis. If presence of latent tuberculosis is established then treatment according to local country guidelines must have been initiated.
- 21. History or current infection with HIV, hepatitis B or hepatitis C.
- 22. History of lymphoproliferative disease or any known malignancy or history of malignancy of any organ system within the past 5 years (except for basal cell carcinoma or actinic keratoses that have been treated with no evidence of recurrence in the past 3 months, carcinoma in situ of the cervix or non-invasive malignant colon polyps that have been removed).
- 23. Current severe progressive or uncontrolled disease which in the judgment of the clinical investigator renders the subject unsuitable for the trial.
- 24. Inability or unwillingness to undergo repeated venipuncture (e.g., because of poor tolerability or lack of access to veins).
- 25. Any medical or psychiatric condition which, in the investigator's opinion, would preclude the participant from adhering to the protocol or completing the study per protocol.
- 26. Donation or loss of 400 mL or more of blood within 8 weeks before randomization.
- 27. History or evidence of ongoing alcohol or drug abuse, within the last six months before randomization.
- 28. Plans for administration of live vaccines during the study period or within 6 weeks preceding randomization.

6 Treatment

6.1 Study treatment

6.1.1 Investigational and control drugs

The following drugs will be used in this study and will be administered in accordance with this protocol. Secukinumab 150 mg syringes for subcutaneous injection will be provided in 1.0 mL pre-filled syringe. Secukinumab placebo for subcutaneous injection will be provided as a 1.0 mL pre-filled syringe matching the appearance of 150 mg secukinumab syringe; each placebo pre-filled syringe contains a mixture of inactive excipients, matching the composition of the secukinumab 150 mg dose.

Participants will be instructed by site staff on how to self-administer the subcutaneous injection using the PFS, based on the Instructions for Use (IFU). The investigational drug will be administered by the participant into the appropriate injection site of the body under the supervision of the site staff. All injections through Week 48 will be performed at the study site. Site staff will administer the injection to those participants who are not able or unwilling to self-administer the PFS injection.

Home administration will be allowed under the situation as described in Section 16.9.

NOTE: The PFS do not need to be prepared at the site. PFS will be packaged both as doubleblind supplies.

The study medication will be labeled as follows:

• Double blind Secukinumab PFS will be labeled as AIN457 150mg/1.0 ml/Placebo

Novartis GCS will supply the following investigational products:

| Investigational/ Control Drug (Name and Strength) | Pharmaceutical Dosage Form | Route of Administration | Supply Type | Sponsor (global or local) |
|--|-------------------------------|----------------------------|--------------|------------------------------|
| Secukinumab 150 | PFS solution for | Subcutaneous | Double Blind | Novartis Pharma |
| mg | injection | Injection | | AG (global) |
| Secukinumab | PFS solution for | Subcutaneous | Double Blind | Novartis Pharma |
| Placebo | injection | Injection | | AG (global) |

 Table 6-1
 Investigational and control drug

6.1.2 Additional study treatments

No additional treatment beyond investigational treatment described in Section 6.1.1 is used in this trial.

6.1.3 Treatment arms/group

Participants fulfilling the inclusion criteria will be randomized to one of the following two groups in a 1:1 ratio, with 20 participants in each of the two groups as depicted below:

- Group 1 : Secukinumab 150 mg s.c. at BSL, Week 1, 2, 3, 4, 8, and 12
- Group 2 : Secukinumab Placebo s.c. at BSL, Week 1, 2, 3, 4, 8, and 12

At Week 16, the participants in Group 1 and Group 2 will be re-randomized in 1:1 ratio separately:

• Group 1 will be re-randomized in 1:1 ratio to:

Secukinumab 150 mg s.c. regimen (1.0 mL PFS of 150 mg dose + 1.0 mL PFS of placebo)

• Group 2 will be re-randomized in 1:1 ratio to:

Secukinumab 150 mg s.c. regimen (1.0 mL PFS of 150 mg dose + 1.0 mL PFS of placebo)

6.1.4 Treatment duration

The overall planned duration of study treatment is 52 weeks, split between Treatment Period 1 (16 weeks) and Treatment Period 2 (36 weeks). Participants may voluntarily discontinue from the study treatment for any reason at any time. (see Section 9.1.1)

6.2 Other treatment(s)

Not applicable.

6.2.1 Concomitant therapy

The investigator should instruct the participant to notify the study site about any new medications (including over-the-counter drugs, calcium, vitamins, herbal medicines and tranditional Chinese medicines) administered after the participant is enrolled into the study. All medications (other than study treatment), procedures and significant non-drug therapies (including physical therapy and blood transfusions) must be recorded on the Prior and Concomitant medications or Procedures and Significant Non Drug Therapy eCRF. The reason, name of the drug, procedure or non-drug therapy should be listed.

Each concomitant drug must be individually assessed against all exclusion criteria/prohibited medication. If in doubt, the Investigator should contact the Novartis medical monitor before reassigning treatment for a participant or allowing a new medication to be started. If the participant is already enrolled, contact Novartis to determine if the participant should continue participation in the study.

6.2.1.1 Permitted concomitant therapy requiring caution and/or action

Participants are permitted to use the medications as described below.

Methotrexate (MTX)

Participants taking MTX (up to 25 mg/week) must be on a stable dose for at least 4 weeks before randomization and maintained stable until Week 16.

Folic acid

Participants on MTX must be taking folic acid supplementation (at the dose permitted by local practice guideline) before randomization and during the trial to minimize the likelihood of MTX associated toxicity.

Cholestyramine for leflunomide wash out

In case of leflunomide treatment, a drug wash out of 8 weeks has to be performed. However, prior to randomization another wash out procedure might be considered. Cholestyramine could be given orally to wash out the drug at a dose of 8 g 3 times a day (t.i.d). Cholestyramine reduced plasma levels of the active leflunomide metabolite by approximately 40% in 24 hours and by 49% to 65% in 48 hours in three healthy volunteers. The administration of cholestyramine is recommended in participants who require a drug elimination procedure. If a participant receives 8 g t.i.d. for 11 days, the wash out period could be 4 weeks (counting from the beginning of the 11 days treatment).

Systemic corticosteroids

Treatment with systemic corticosteroids is permitted up to a maximum daily dosage of 10 mg prednisone equivalent and if the dose was stable within the 2 weeks preceding randomization. The participant should remain on a stable dose until Week 16.

Corticosteroid dose reductions below 10 mg prednisone equivalent are permitted after Week 16 assessment, although the corticosteroid dose should not be reduced more than 1 mg prednisone equivalent every 4 weeks.

Any change in the dose of systemic corticosteroids during the trial must be recorded on the corresponding eCRF page.

Intra-articular corticosteroids are not permitted within the 4 weeks preceding randomization and up to Week 16. After Week 16 assessment, no more than 1 joint per 24-week period may be injected. No single injection should exceed 40 mg of triamcinolone (or equivalent) and the total dose of intra-articular corticosteroid may not exceed 80 mg of triamcinolone (or equivalent).

Non-steroidal anti-inflammatory drugs (NSAIDs) [including cyclooxygenase-1 (COX-1) or cyclooxygenase-2 (COX-2) inhibitors], low strength opioids and acetaminophen/paracetamol

Participants on regular use of NSAIDs, low strength opioids, or paracetamol/acetaminophen as required (PRN) should be on stable dose for at least 2 weeks before randomization to allow inclusion. They should remain on a stable dose in the study up to Week 16, however, they have to refrain from any intake during at least 24 hours before a visit with disease activity assessment.

After Week 16 assessments are completed, a change in the NSAIDs, low strength opioids, or paracetamol/acetaminophen treatment regimen is permitted.

Any change of the NSAIDs, low strength opioids, or paracetamol/acetaminophen treatment during the trial should be recorded on the corresponding eCRF page.

Note: Background and concomitant medications will not be provided by Novartis and must be supplied by the the study center.

6.2.2 Prohibited medication

Use of the treatments displayed in the below table are not allowed after Screening (Visit 1). The minimum required period without prohibited treatment before Screening (Visit 1) is also listed in Table 6-2. Each concomitant drug must be individually assessed against all exclusion criteria and the table below to see if it is allowed. If in doubt, the investigator should contact Novartis or delegate before randomizing a participant or allowing a new medication to be started.

Live vaccines should not be given until 12 weeks after last study treatment administration.

| Medication | Prohibition period | Action taken | |
|---|--|---|--|
| Biological immunomodulating agents > 3 different TNFα | No prior use allowed | Discontinue from study | |
| Other biological immunomodulating agents except for those targeting TNFα (such as Ustekinumab) | | Discontinue from study | |
| Etanercept ¹ | a) 4 weeks prior to randomization b) Treatment period c) Follow up period | a) Delay randomization to achieve 4-week wash out or discontinue from study b) Discontinue study treatment c) Stop prohibited treatment | |
| Infliximab ¹ | a) 8 weeks prior to randomization b) Treatment period c) Follow up period | a) Delay randomization to achieve 8-week wash out or discontinue from study b) Discontinue study treatment c) Stop prohibited treatment | |
| Adalimumab, golimumab, certolizumab ¹ | a) 10 weeks prior to randomization b) Treatment period c) Follow up period | a) Delay randomization to achieve 10-week wash out or discontinue from study b) Discontinue study treatment c) Stop prohibited treatment | |
| Unstable dose of MTX ² | a) 4 weeks prior to randomization b) Treatment period up to Week 16 | a) Delay randomization to achieve 4-week stable dose or discontinue from study b) Keep MTX at a stable permitted dose from at least 4 weeks before randomization up to Week 16, otherwise, discontinue study treatment | |
| DMARDs (except MTX) | a) 4 weeks prior to randomization b) Treatment period c) Follow up period | a) Delay randomization to achieve 4-week wash out or discontinue from study b) Stop prohibited treatment or discontinue study treatment c) Stop prohibited treatment | |
| Leflunomide | a) 8 weeks prior to randomization b) Treatment period c) Follow up period | a) Delay randomization to achieve 8-week wash out or discontinue from study b) Stop prohibited treatment or discontinue study treatment c) Stop prohibited treatment | |

 Table 6-2
 Prohibited medication

Novartis Clinical Trial Protocol (Version No. 00)

| Medication | Prohibition period | Action taken |
|---|---|--|
| Leflunomide with Cholestyramine washout | a) 4 weeks prior to randomization b) Treatment period c) Follow up period | a) Delay randomization to achieve 4-week wash out or discontinue from study b) Stop prohibited treatment or discontinue study treatment c) Stop prohibited treatment |
| Apremilast | a) 4 weeks prior to randomization b) Treatment period c) Follow up period | a) Delay randomization to achieve 4-week wash out or discontinue from study b) Stop prohibited treatment or discontinue study treatment c) Stop prohibited treatment |
| Unstable dose of NSAIDs (including COX-1 or COX-2 inhibitors), low strength opioids and paracetamol/acetaminophen ² | a) 2 weeks prior to randomization b) Treatment period up to Week 16 | a) Delay randomization to achieve 2-week stable dose or discontinue from study b) Keep NSAIDs, low strength opioid and paracetamol/acetaminophen at a stable dose from at least 2 weeks before randomization up to Week 16, otherwise, discontinue study treatment |
| Unstable dose of systemic corticosteroids <= 10 mg prednisone equivalent ² | a) 2 weeks prior to randomization b) Treatment period up to Week 16 | a) Delay randomization to achieve 2-week stable dose or discontinue from study b) Keep systemic corticosteroids (<= 10 mg prednisone equivalent) from at least 2 weeks before randomization up to Week 16, otherwise, discontinue study treatment |
| Systemic corticosteroids > 10 mg prednisone equivalent ² | a) 2 weeks prior to randomization b) Treatment period c) Follow up period | a) Delay randomization to achieve 2-week wash out or discontinue from study b) Stop prohibited treatment or discontinue study treatment c) Stop prohibited treatment |
| Intra-articular injections ² | a) 4 weeks prior to randomization b) Treatment period up to Week 16 c) Treatment period after Week 16 assessment to Week F60 | a) Delay randomization to achieve 4-week wash out or discontinue from study b) Discontinue study treatment c) No more than 1 joint per 24- week period is permitted after Week 16 assessment to Week F6 |
| Intramuscular or intravenous corticosteroid treatment | a) 4 weeks prior to randomization b) Treatment period c) Follow up period | a) Delay randomization to achieve 4-week wash out or discontinue from study b) Stop prohibited treatment or discontinue study treatment c) Stop prohibited treatment |
| Any investigational treatment or participation in any interventional trial | a) 4 weeks or 5 half-lives (which is longer) prior to randomization b) Treatment period c) Follow up period | a) Delay randomization to achieve wash out or discontinue from stud b) Discontinue study treatment c) Stop prohibited treatment |

| Medication | Prohibition period | Action taken |
|---|---|--|
| Live vaccinations | a) within 6 weeks preceding randomization randomization b) Treatment period c) Follow up period | a) Delay randomization to achieve wash out or discontinue from study b) Interrupt study treatment for 12 weeks, or discontinue study treatment (see details in Section 6.5) c) Stop prohibited treatment |
| Oral or topical retinoids | a) 4 weeks prior to randomization b) Treatment period c) Follow up period | a) Delay randomization to achieve 4-week wash out or discontinue from study b) Stop prohibited treatment or discontinue study treatment c) Stop prohibited treatment |
| Photochemotherapy (e.g. PUVA) | a) 4 weeks prior to randomization b) Treatment period c) Follow up period | a) Delay randomization to achieve 4-week wash out or discontinue from study b) Stop prohibited treatment or discontinue study treatment c) Stop prohibited treatment |
| Phototherapy [ultraviolet A (UVA) or ultraviolet B (UVB)] | a) 2 weeks prior to randomization b) Treatment period c) Follow up period | a) Delay randomization to achieve 2-week wash out or discontinue from study b) Stop prohibited treatment or discontinue study treatment c) Stop prohibited treatment |
| Topical skin treatments (except in face, eyes, scalp and genital area during screening, only corticosteroids with mild to moderate potency) | a) 2 weeks prior to randomization b) Treatment period c) Follow up period | a) Delay randomization to achieve 2-week wash out or discontinue from study b) Stop prohibited treatment or discontinue study treatment c) Stop prohibited treatment |
| Traditional Chinese medicine treatments of psoriasis and/or psoriatic arthritis ³ | a) 4 weeks prior to randomization b) Treatment period up to Week 16 c) Treatment period after Week 16 assessment to Week F60 | a) Delay randomization to achieve 4-week wash out or discontinue from study b) Stop prohibited treatment or discontinue study treatment c) Stop prohibited treatment |

1. These agents fall under the category of biologic immunomodulators and are prohibited medications. Administration of these agents requires study discontinuation (see Section 9.1.1).

2. See details in Section 6.2.1

3. Traditional Chinese medicine (TCM) is defined as a compendium of methods popular in Chinese tradition for the treatment of a wide range of conditions. TCM practitioners use herbal remedies, acupuncture, massage, mind-body and dietary therapies, and other methods.

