Placebo (1.0 mL PFS) administered at BSL, Weeks 1, 2 and 3, followed by dosing every four weeks starting at Week 4.

At Week 16, the participants in Group 1 and Group 2 will be re-randomized in a blinded manner in 1:1 ratio separately:

- The participants in Group 1 will be re-randomized in 1:1 ratio to secukinumab 150 mg s.c. q4w regimen (1.0 mL PFS of 150 mg dose + 1.0 mL PFS of placebo)
- The participants in Group 2 will be re-randomized in 1:1 ratio to secukinumab 150 mg s.c. q4w regimen (1.0 mL PFS of 150mg dose + 1.0 mL PFS of placebo) or

A primary endpoint analysis will be conducted after all participants complete Week 16 visit. Rescue medication will not be allowed before the completion of Week 16 assessments (Section 6.2.3). Although no participant will be restricted from receiving necessary rescue medications for lack of benefit or worsening of disease, if rescue with prohibited biologics (as described in Section 6.2.2) occurs prior to completion of Week 16 assessments, participants will be discontinued from the study treatment and will enter into the follow-up period after an End of Study visit. Safety and efficacy will be assessed in detail at every study visit, and participants who are deemed not to be benefiting from the study treatment based upon safety and efficacy assessments by the investigator, or for any reason of their own accord, are free to discontinue participation in the study at any time.

A follow-up visit will be done 12 weeks after last study treatment administration for all participants, regardless of whether they complete the entire study as planned or discontinue prematurely.

The total combined duration of treatment for this Phase III study is 52 weeks.

[figure not shown]

Figure 3-1 Study design

4 Rationale

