6.2.3 Rescue medication

Rescue medication is defined as any new therapeutic intervention or a significant change to ongoing therapy made because a participant is experiencing either no benefit from participation in the trial or worsening / exacerbation of their disease.

Rescue medication must not be used before completion of Week 16 assessments (see Section 3). Each concomitant drug must be individually assessed against all exclusion criteria and prohibited medication (Table 6-2).

When in doubt the Investigator should contact the Novartis medical monitor before treatment reassignment or allowing a new medication to be started. If any of the medications listed in Table 6-2 is deemed a necessary rescue therapy, the Investigator must follow the actions to be taken outlined in this section. Rescue treatment is to be provided by the study center or personal physician.

Please see Section 6.2.1 and Section 6.2.2 for details. Although no participant will be restricted from receiving necessary rescue medications for lack of benefit or worsening of disease, if rescue with prohibited treatments (as described in Table 6-2) occurs, participants will be discontinued from study treatment and continue to the follow-up visit. Efficacy will be assessed in detail at every study visit, and participants who are deemed not to be benefiting from the study treatment based upon safety and efficacy assessments by the investigator or for any reason on their own accord are free to discontinue participation from the treatment at any time.

6.3 **Participant numbering, treatment assignment, randomization**

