1.1 Study design

This bridging study uses a randomized, double-blind, placebo-controlled, parallel-group design to assess the efficacy, safety, and tolerability of secukinumab 150 mg s.c. in Chinese participants with active PsA.

A screening period running up to 10 weeks before randomization will be used to assess participant eligibility followed by 52 weeks of treatment.

At BSL, approximately 40 Chinese participants whose eligibility are confirmed will be randomized to one of two treatment groups in 1:1 ratio:

- Group 1 – secukinumab 150mg s.c.:

Secukinumab 150 mg (1.0 mL PFS of 150 mg dose) administered at BSL, Weeks 1, 2, and 3 followed by dosing every four weeks starting at Week 4.

- Group 2 – placebo s.c.

Placebo (1.0 mL PFS) administered at BSL, Weeks 1, 2 and 3, followed by dosing every four weeks starting at Week 4.

At Week 16 the participants in Group 1 and Group 2 will be re-randomized in a blinded manner in 1:1 ratio separately.

- The participants in Group 1 will be re-randomized in 1:1 ratio to secukinumab 150 mg s.c. q4w regimen (1.0 mL PFS of 150 mg dose + 1.0 mL PFS of placebo) or secukinumab [REDACTED] s.c. q4w regimen ([REDACTED])
- The participants in Group 2 will be re-randomized in 1:1 ratio to secukinumab 150 mg s.c. q4w regimen (1.0 mL PFS of 150 mg dose + 1.0 mL PFS of placebo) or secukinumab [REDACTED] s.c. q4w regimen ([REDACTED])

Stratification is not applicable in the study.

A primary endpoint analysis was conducted after all participants complete Week 16 visit. Rescue medication was not allowed before the completion of Week 16 assessments (protocol Section 6.2.3). Although no participant will be restricted from receiving necessary rescue medications for lack of benefit or worsening of disease, if rescue with prohibited biologics (as described in section 6.2.2) occurs prior to completion of Week 16 assessments, participants will be discontinued from the study treatment. Efficacy will be assessed in detail at every study visit, and participants who are deemed not to be benefiting from the study treatment based upon safety

and efficacy assessments by the investigator, or for any reason of their own accord, are free to discontinue participation in the study at any time.

[figure not shown]
A follow-up visit will be done 12 weeks after last study treatment administration for all participants, regardless of whether they complete the entire study as planned or discontinue prematurely.

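### For a non-rescue IM/IV or >10 mg systemic steroid shortly before Week 16, the action taken, not the exposure, can decide whether ACR20 is scored as observed or as non-response

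*Protocol*

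**What the plan says.** **Action for steroid use.** Table 6-2 (Protocol 6.2.2) treats steroid exposures differently during the placebo-controlled period.

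- IM/IV steroid, and systemic steroid above 10 mg prednisone equivalent: "b) Stop prohibited treatment or discontinue study treatment c) Stop prohibited treatment". No criterion is given for choosing between the two.
- Intra-articular injection up to Week 16: "b) Discontinue study treatment c) No more than 1 joint per" (the one-joint allowance applies only after Week 16).
- Systemic steroid of 10 mg or less: the dose must stay stable to Week 16, failing which study treatment ends.

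**Entry washout.** Exclusion criteria 7 and 8 (Protocol 5.2) give both injection routes the same window: "Any intramuscular or intravenous corticosteroid treatment within 4 weeks before randomization" and "Any therapy by intra-articular injections (e.g., corticosteroid) within 4 weeks before randomization". Table 6-2 sets 2 weeks for systemic steroid above 10 mg.

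**Rescue.** Protocol 6.2.3: "Rescue medication is defined as any new therapeutic intervention or a significant change to ongoing therapy made because a participant is experiencing either no benefit", or worsening of disease. The consequence is that "if rescue with prohibited treatments (as described in Table 6-2) occurs, participants will be discontinued from study treatment". Protocol Section 3 is narrower: "if rescue with prohibited biologics (as described in Section 6.2.2) occurs prior to completion of Week 16 assessments, participants will be discontinued". SAP 1.1 repeats the narrower wording.

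**Other routes to discontinuation.** Section 9.1.1 requires it for prohibited treatment in line with 6.2.2. Separately, it requires it for a severe or serious adverse event incompatible with study medication, including one that needs an unacceptable co-medication. Section 6.2.1 tells sites to contact the sponsor about whether an enrolled participant should continue.

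**Scoring.** The primary estimand (2.1) names one intercurrent event, discontinuation from treatment or study. Section 12.4.3 and SAP 2.5.1 assign non-response for discontinuation, missing data or unblinding. None of the three mentions prohibited medication.

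**The concern.** A single IM or IV dose is over once given, so stopping it afterwards changes nothing. A dose after Week 12 is still inside the protocol's 4-week washout at the Week 16 assessment. The protocol regards that exposure as close enough to disease assessment to bar entry, yet it can leave the participant on study treatment with the ACR20 result taken at face value. Had study treatment been discontinued for the same exposure, the same participant would be a non-responder.

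The contrast within the table suggests this was not intended: a small change in a low oral dose ends study treatment, while a larger systemic or parenteral dose need not.

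The trial relies on an estimate and its interval from about 20 participants per arm, so one score is visible in the result. The planned sensitivity analyses in 12.4.4 concern model assumptions and missing data. A participant kept on treatment with complete Week 16 data is not missing, so those analyses do not reach this case.

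**Working it through.** **1. Which cases remain open**

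| Situation before Week 16 | Governing text | Option open? |
|---|---|---|
| Steroid for lack of benefit or worsening of PsA | 6.2.3 | No, discontinue |
| Steroid for a severe or serious AE caught by 9.1.1 | 9.1.1 | No, discontinue |
| Background steroid of 10 mg or less raised above 10 mg | Two Table 6-2 rows apply | Unclear; the lower-dose row may already require discontinuation |
| Other non-rescue IM/IV or >10 mg steroid, no background steroid | Table 6-2; 9.1.1 refers back to it | Yes |

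Only the last row is clearly open. It bears on ACR20 mainly when the dose falls within 4 weeks (IM/IV) or 2 weeks (>10 mg) of the Week 16 assessment.

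**2. Reproducing the plan's figure**

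Inputs (Protocol 12.8.1): 20 per arm, response rates 0.514 and 0.231, threshold 0.1415. X1 and X2 are the responder counts on secukinumab and placebo, X1 ~ Bin(20, 0.514) and X2 ~ Bin(20, 0.231). Summing exactly over all pairs:

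- P((X1 − X2)/20 > 0.1415) = P(X1 − X2 ≥ 3) = 0.860
- P(X1 − X2 > 0) = 0.960

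Both match Table 12-1.

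**3. Effect of one such participant**

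The documents give no frequency of steroid use, so one user is an assumption. Each reclassified responder moves that arm's rate by 1/20 = 5 points. Fix the user's score, keep the other 19 in that arm binomial, and recompute P(difference > 14.15 points):

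| User's arm | Non-responder | Kept, responds at arm rate | Kept, certain to respond |
|---|---|---|---|
| Placebo | 0.879 | 0.860 | 0.797 |
| Secukinumab | 0.822 | 0.860 | 0.896 |

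The direction depends on the arm. Certain response is an upper bound.

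**4. When the choice moves the estimate across 14.15 points**

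- Placebo responder recounted: only if the as-observed count difference is 2 (10 points, becoming 15). Probability 0.082 given response; × 0.231 = 0.019.
- Secukinumab responder recounted: only if the as-observed count difference is 3 (15 points, becoming 10). Probability 0.075 given response; × 0.514 = 0.038.

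**5. Effect on the estimate and interval**

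Illustrative counts, unadjusted for weight; Wald 95% CI = d ± 1.96 × √[p1(1 − p1)/20 + p2(1 − p2)/20].

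| Secukinumab vs placebo | Difference | 95% CI |
|---|---|---|
| 10/20 vs 5/20 (as observed) | 25 points | −4.0 to 54.0 |
| 10/20 vs 4/20 (one placebo responder recounted) | 30 points | 1.9 to 58.1 |
| 9/20 vs 5/20 (one secukinumab responder recounted) | 20 points | −8.9 to 48.9 |

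**The case against.** The strongest reply is that little discretion is left. Rescue ends study treatment under 6.2.3, 9.1.1 removes many adverse-event cases, the lower-dose row may cover background users, the sponsor is brought in under 6.2.1, and decisions are made blinded. All of that stands, and it is why the point is confined to the last row of the first table. It does not close that row: sponsor contact and blinding limit arm-directed choice, but neither says how to score the participant.

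Using observed data after a brief steroid for an unrelated illness is also a defensible strategy. That stands too, and is a reason not to change the primary rule.

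SAP 2.3.1 tabulates protocol deviations, and SAP 2.4.2 summarises glucocorticoid use. These may show an imbalance, but they do not isolate use shortly before Week 16 or rescore ACR20.

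The 14.15-point figure belongs to the sample-size section. Section 12.4 sets no decision on it and the trial runs no formal test, so the threshold probabilities above describe sensitivity and not a changed verdict.

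Finally, missing-data rules and supportive analyses sit in the SAP for the primary analysis (SAP 2.5.3 and 2.5.4), which is not among the documents. It may already deal with this.

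Three stronger readings are tempting and not supported:

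- *A steroid given for a PsA flare can be kept because Section 3 and SAP 1.1 mention only biologics.* Section 6.2.3 extends the rule to everything in Table 6-2, and 12.4.3 then makes the participant a non-responder.
- *The same gap matters for DMARDs, apremilast or traditional Chinese medicine.* Those rows carry the same action, but their use for lack of benefit or worsening is rescue and already settled.
- *Sites can steer the result.* They are blinded, and the sponsor is to be consulted.

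**Conclusion.** The point holds in a narrow form. For a non-rescue IM/IV or >10 mg systemic steroid not caught by 9.1.1, clearest without background steroid, the plan permits two actions and lets the one taken fix the ACR20 score. A response inside the protocol's own washout can then count as a treatment response.

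Each such responder is worth 5 points in one arm. With one assumed user responding at the arm rate, the chance that the choice carries the estimate across 14.15 points is 1.9% (placebo) or 3.8% (secukinumab). With no users there is no effect. These figures rest on the design rates, 20 per arm and no weight adjustment. The documents do not show that any such participant exists or that the reported result is biased. Confidence is medium, chiefly because the primary-analysis SAP is unseen.

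**What to change.** Leave the primary rule unchanged. Week 16 has been analysed, and under Protocol 4.4 the sponsor's clinical team is unblinded for Period 1 after the Week 16 lock.

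1. From the concomitant-medication data, list by arm the participants who had an IM/IV steroid within 4 weeks, or a systemic steroid above 10 mg within 2 weeks, before the Week 16 assessment and stayed on study treatment.
2. Present the ACR20 difference and 95% CI with these participants scored as observed and again as non-responders, labelled post hoc, unless the primary-analysis SAP already did so.
3. If the list is empty, say so; nothing further is needed.

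The cost is one listing and one additional run of the ACR20 model, with no amendment and no new data. The downside is that a participant treated briefly for an unrelated illness counts as a non-responder in one of the two versions.
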